21.12 Appendix 12: Response Criteria for HCL

Response status for hairy cell leukemia (HCL) will be assessed according to the following criteria adapted from the NCCN guideline - Consensus Resolution, and previous HCL studies.

Complete response (CR) with or without Minimal Residual Disease (\pm MRD):

- No evidence of leukemic cells by routine and H/E stains of the peripheral blood and bone marrow (BM).
- MRD: CR with HCL evident in blood by flow cytometry (FACS) or in BM biopsy by immunohistochemistry (IHC)
- No hepatomegaly, splenomegaly, or abnormal ($< 2\text{cm}$ minimum length) lymphadenopathy by appropriate radiographic techniques.
- **NOTE:** Enlarged liver or spleen associated with a negative nuclear medicine study will not prevent consideration of CR for those subjects meeting all other criteria.
- Normal complete blood count (CBC) as exhibited by: absolute neutrophil count (ANC) $\geq 1.5 \times 10^9/\text{L}$, platelets $\geq 100 \times 10^9/\text{L}$, and hemoglobin $\geq 11 \text{ g/dL}$ without transfusions or growth factors for at least 4 weeks.

After this 4-week period, BM biopsy and computed tomography (CT) scan must be performed to confirm CR. The BM biopsy and aspirate need not be performed at the beginning of this 4-week interval.

Complete response (CR): defined as the complete disappearance of all evidence of disease and requires all of the following:

- Normal CBC as exhibited by: ANC $\geq 1.5 \times 10^9/\text{L}$, platelets $\geq 100 \times 10^9/\text{L}$ and hemoglobin $\geq 11 \text{ g/dL}$
- Absence of hairy cells (by morphological examination) in the peripheral blood and in the BM
- Regression to normal of disease-related organomegaly

Confirmation of CR: At the confirmatory ≥ 6 month visit, a BM biopsy, hematology, immunoglobulins and flow cytometry will be reassessed.

Duration of CR: The duration of complete remission is calculated from the time of achievement of all criteria of CR to the time of relapse from CR.

Partial response (PR): requires all of the following for a period of at least 4 weeks:

- Normal peripheral blood counts (as in CR)
 - $ANC \geq 1.5 \times 10^9/L$ or 50% improvement over baseline without growth factors for at least 4 weeks, **AND**
 - Platelets $\geq 100 \times 10^9/L$ or 50% improvement over baseline, **AND**
 - Hemoglobin ≥ 11 g/dL or 50% improvement over baseline without transfusions or growth factors for at least 4 weeks.

NOTE: For subjects who are transfusion-dependent at baseline, a hemoglobin of ≥ 9 g/dL without transfusions or growth factors for at least 4 weeks.

- circulating hairy cells $\leq 5\%$ of lymphocytes
- $\geq 50\%$ reduction of BM infiltration by hairy cells
- $\geq 50\%$ reduction of palpable disease-related organomegaly.

Subject must have the following (if abnormal prior to treatment):

- $\geq 50\%$ decrease or normalization ($< 5000/mm^3$) in peripheral blood lymphocyte count from the pre-treatment baseline value
- $\geq 50\%$ reduction in lymphadenopathy, based on sum of products of perpendicular diameters, or resolution to size consistent with CR
- $\geq 50\%$ reduction in abnormal hepatosplenomegaly by imaging, or resolution to size consistent with CR

Minor response (MR): requires all of the following:

- $\geq 50\%$ reduction of circulating hairy cells

- Improvement of one or more of the peripheral blood counts (ANC, platelets or hemoglobin).

Relapse: defined as the reappearance of leukemia/lymphoma in a subject who previously achieved a CR or documentation of PD in a subject who previously achieved a PR

Stable Disease (SD): defined as not meeting the criteria for CR, PR, MR or PD

Disease progression (PD): defined as the occurrence of at least one of the following compared to pre-treatment:

- $\geq 50\%$ increase in the sum of the products of the greatest perpendicular dimensions of at least two lymph nodes on two consecutive examinations at least 2 weeks apart (at least one node must be ≥ 2 cm in minimum length) or appearance of new palpable lymph nodes
- $\geq 50\%$ increase in the absolute number of circulating lymphocytes, on two consecutive examinations showing abnormal lymphocytosis at least 2 weeks apart
- $\geq 25\%$ decrease in hemoglobin (must be $< 10\text{g/dL}$), platelets (must be $< 100,000/\text{uL}$), or ANC (must be $< 1500/\text{uL}$) unless these are judged to be effects of treatment.

References:

Kreitman RJ, Fitzgerald DJ, Pastan I. Approach to the patient after relapse of hairy cell leukemia. *Leuk Lymphoma*. 2009a;50(suppl 1):32-37.

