29. **NSGCT/NGGCT ONLY: AFP, B-HCG and LDH are the disease assessment markers for the NSGCT/NGGCT cohort.** LDH result obtained from clinical chemistry panel can be used as a tumor marker result. Regardless of baseline values of AFP, β -HCG and LDH, a blood sample will be drawn every 4 weeks for first 48 weeks of study treatment, then every 8 to 12 weeks thereafter, and at the time of disease progression. Synchronize the collection of the blood sample with the imaging schedule.
30. **BTC/ASI ONLY:** A blood sample will be drawn to assess CEA and CA 19-9 every 4 weeks for first 48 weeks of study treatment, then every 8 to 12 weeks thereafter, and at the time of disease progression. Synchronize the collection of the blood sample with the imaging schedule.
31. **HCL ONLY: All required disease assessments necessary for a post-baseline response determination should be performed every 4 weeks (+/- 3 days) for the first 48 weeks of study treatment. Beyond 48 weeks, patients tolerating study drug in the judgement of the treating investigator may transition to a response assessment evaluation interval of at least every 12 weeks (+/- 3 days) (Changed from "at least every 8 weeks (+/- 3 days)" indicated in Protocol Amendments 8 through 11). Patients that are not tolerating study drug in the judgement of the treating investigator must continue (or return to) response assessment evaluation every 4 weeks (+/- 3 days). Assessments must be collected in agreement with those required in the response criteria (please consult Appendix 12).**
32. **HCL ONLY: BM biopsy and aspiration with H/E stain and IHC will be performed when blood counts are consistent with CR or PR for 4 weeks (please consult Appendix 12). If a patient has a PR, and then blood counts become consistent with a CR for 4 weeks, a repeat BM aspirate and biopsy is required to assess a response of CR. Following best response, a bone marrow biopsy and aspirate must be performed every 6 months for two time intervals, then after a year for two time intervals, then every two years.**

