CR-MRD, CR+MRD, PR, MR	
 • Two consecutive assessments are required. A confirmatory disease assessment should be performed no less than 4 weeks (28 days) from the time of initial CR - MRD, CR + MRD, PR or MR. • If a response of any type (CR-MRD, CR+MRD, PR, MR) is assessed and the consecutive assessment is a response of lower magnitude then the confirmed response corresponds with the latter assessment which is the response of lower magnitude. For example, a PR followed by MR results in a confirmed MR response. • The ordering of response magnitude from high to low is CR- MRD, CR+ MRD, PR, MR. • Confirmed responses in this category cannot be assigned for assessments after a patient has an overall response assessment of PD.
SD	
 • SD does not need to be confirmed by a second assessment if the disease assessment meets the criteria after first dose of study drug at a minimum interval of 4 weeks (28 days). If the minimum time for SD is not met, the best response will depend on the subsequent assessments or will be NE. For example, if an assessment of SD is followed by PD and SD does not meet the minimum time requirement, the best response will be PD. When the only assessment (other than NE) after initiation of treatment is SD and the minimum time for SD is not met, the best confirmed response is NE. • If an assessment in the following categories (CR-MRD, CR+MRD, PR, MR) is followed by SD or PD, and the timing of the initial assessment is greater than or equal to 4 weeks after the first dosing, then the confirmed response is SD. • If there is 1 assessment in the following categories (CR-MRD, CR+MRD, PR, MR) and the timing of the assessment is greater than or equal to 4 weeks after the first dosing, and consecutive assessments are either missing, not done or NE then the confirmed response is SD. • Confirmed responses in this category cannot be assigned for assessments after a patient has an overall response assessment of PD.
PD	
 • PD does not need to be confirmed by a second assessment of PD to confirm PD as the best response. When the only assessment (other than NE) at any point after initiation of treatment is PD the confirmed response is PD.

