DoR based on the investigator response will be summarized for ATC, BTC, ASI, WHO Grade 1 or 2 Glioma, WHO Grade 3 or 4 Glioma and HCL cohorts. If data warrant, Kaplan-Meier method will be used to summarize DoR descriptively and graphically. The median DoR and the first and third quartiles will be presented, along with corresponding 95% confidence intervals. Brookmeyer-Crowley method will be used for the confidence interval calculation. DoR will also be summarized at 6 months, 12 months and 24 months.

Listing of DoR based on investigator assessment will also be provided.

In addition, swim lane plots will be generated for response data based on investigator assessment. These plots will present the best confirmed response category, duration of treatment, time of the first response, duration of response, time of the first disease progression based on radiological assessment and study treatment status at the time of data cut-off for the analysis.

As a sensitivity analysis, DoR based on independent radiology review will be summarized and listed for the ATC, BTC, WHO Grade 1 or 2 Glioma, and WHO Grade 3 or 4 Glioma cohorts, including the estimated median, first and third quartiles, 6 and 12 month Kaplan-Meier estimates. The derivation of DoR based on independent radiology review is similar to that based on the investigator assessment.

For the HCL cohort only, and for the subset of subjects who have a confirmed complete response (with or without MRD), the complete response duration will be calculated as the time from first CR until the earliest of the first subsequent non-CR adequate assessment or death due to any cause. Censoring rules will be applied the same as with Duration of Response. Kaplan-Meier estimates will be used to estimate the median and quartiles of the complete response duration as well as the complete response duration at 180 days. The number and proportion of

the ITT population with complete response duration of at least 180 days will be calculated along with the corresponding Clopper-Pearson exact confidence interval. The time to first confirmed complete response and time to first confirmed overall response will both be summarized with the minimum, maximum, 1st and 3rd quartiles and median displayed in weeks. Only confirmed responders will be included in each of the summaries.

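### For hairy cell leukemia, SAP 2.6.1 ends complete response at the first non-CR assessment or death, Appendix 12 ends it at relapse, and no change is declared; Appendix 12's two CR confirmation rules also need reconciling

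*Protocol*

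**What the plan says.** **End of CR.** Appendix 12 of the protocol (Response Criteria for HCL) measures CR duration "from the time of achievement of all criteria of CR to the time of relapse from CR". It defines relapse after a CR as leukemia or lymphoma coming back, and does not mention a fall in counts there. Count falls appear under disease progression, where those judged to be treatment effects are set aside. SAP 2.6.1, for HCL subjects with a confirmed CR with or without minimal residual disease (MRD), runs from first CR to "the earliest of the first subsequent non-CR adequate assessment or death due to any cause". SAP 4.2 treats an assessment as adequate if its response is neither missing nor not evaluable.

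**What is reported.** SAP 2.6.1 gives Kaplan-Meier quartiles and a 180-day estimate for CR duration. It also gives the number and proportion of the ITT population with CR of at least 180 days, with an exact interval. SAP Section 3 declares no departure from the protocol's analyses.

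**Confirmation.** Appendix 12 has two passages. Under CR with or without MRD, counts must be normal and unsupported for four weeks: "After this 4-week period, BM biopsy and computed tomography (CT) scan must be performed to confirm CR". Under a second CR definition with no MRD split, a confirmatory visit follows at six months or more, at which "a BM biopsy, hematology, immunoglobulins and flow cytometry will be reassessed". SAP Table 2-4 asks for two consecutive assessments, the second "no less than 4 weeks (28 days) from the time of initial CR - MRD, CR + MRD, PR or MR", and names neither marrow nor CT. Footnote 32 of protocol Section 7.1 places marrow at the point where counts have fitted a response for four weeks, and then: "Following best response, a bone marrow biopsy and aspirate must be performed every 6 months for two time intervals".

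**The concern.** Relapse and a non-CR reading are different events. CR in Appendix 12 needs ANC of at least 1.5, platelets of at least 100 (both × 10⁹/L) and hemoglobin of at least 11 g/dL. One count below a cut-off can therefore make a visit non-CR with no leukemia present. Neutropenia is on the SAP's list of adverse events of special interest, so such readings on treatment are plausible.

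At stake are the HCL CR duration curve and the 180-day proportion. A reader will assume that both follow Appendix 12, because Section 3 reports no change. On confirmation, the reader cannot tell which of the protocol's two rules the SAP's confirmed CR represents.

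**Working it through.** There is no sample size, power or event count on this point to reproduce. The check compares texts, with illustrations under stated assumptions.

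1. **End rules compared.** A relapse visit is itself a non-CR assessment, so the SAP's end date is never later than the Appendix 12 end date. For each subject, CR duration under the SAP is the same or shorter. It is shorter when a visit loses CR on counts alone before any relapse. Death is a further event that SAP 2.6.1 includes and Appendix 12 does not name.

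2. **Is the end event delegated?** Protocol 18.3.3.2 leaves further confirmation details and the censoring rules for duration of response to the analysis plan. It does not leave open the event that ends CR.

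3. **Possible size of the end-rule effect (assumed rates).** Assessments are every 4 weeks for the first 48 weeks. Since 6 × 28 = 168 days, six visits fall within 180 days of first CR. Let q be the chance that a visit is non-CR without relapse, independent between visits. The share of CRs ended by such a reading is 1 − (1 − q)^6:
   - q = 1%: 1 − 0.99^6 = 6%
   - q = 2%: 1 − 0.98^6 = 11%
   - q = 5%: 1 − 0.95^6 = 26%
   - q = 10%: 1 − 0.90^6 = 47%

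   If the visit at about day 28 is the confirming one and must itself be CR, five visits remain. The formula 1 − (1 − q)^5 then gives 5%, 10%, 23% and 41%.

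4. **Confirmation intervals.** The SAP interval is 4 × 7 = 28 days, equal to the four-week period in Appendix 12's first rule. Six months is 6 × 30.4375 = 182.6 days, and 182.6 / 28 = 6.5 times longer. The SAP's HCL categories, CR without MRD and CR with MRD, belong to the first definition. Both Appendix 12 rules require marrow, and the first also requires CT; Table 2-4 names neither.

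5. **How much the choice of rule could matter (assumed exponential CR duration).** The share of CRs confirmed at 28 days that are still CR at 182.6 days is exp[−ln 2 × (182.6 − 28) / (30.4375 × m)] for a median of m months. This gives 56% for m = 6, 75% for m = 12, 86% for m = 24 and 94% for m = 60.

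6. **Weight of one subject.** The Amendment 11 rationale counts 36 HCL subjects on treatment and 7 in follow-up, so the ITT HCL cohort has at least 36 + 7 = 43. One subject moves an ITT proportion by at most 1/43 = 2.3 percentage points.

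**The case against.** **The outputs are supplementary.** Neither CR rate nor CR duration is listed in the protocol's objectives and endpoints table, so Section 3 may be literally true of the analyses listed there. The listed endpoint, duration of response, agrees with the protocol: SAP 2.6.1 counts HCL relapse as progression. That limits the importance of the point. It does not remove it, because Appendix 12 defines CR duration and the SAP reports it under a different rule.

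**Confirmation was left to the analysis plan, and 28 days matches one of the protocol's own rules.** Both statements stand. A reader who looks only at the six-month passage might infer that the SAP overstates the HCL CR rate. The documents do not support that, since the four-week rule sits under the category that the SAP uses. Nor do they support reading confirmed CR as resting on blood alone. Protocol 7.1 schedules marrow and flow cytometry when counts fit a response for four weeks, repeats them when a partial response moves to CR, and schedules CT at the same count trigger. What stands is that Table 2-4 names no marrow or CT at the second assessment.

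**The 180-day proportion already covers durability near six months.** It does so only in part. It uses the SAP's own end rule, so it cannot stand in for either the relapse rule or a six-month check with marrow.

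**HCL responses are described as durable.** The Amendment 11 rationale says so, which may mean that few CRs are lost early. It gives no visit-level data on isolated count falls.

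**Conclusion.** The CR-duration mismatch holds on the text, is undeclared, and runs in one direction for each subject. Its size is unknown. The 6% to 47% range rests on assumed rates of 1% to 10% per visit, independence between visits, and investigators recording a count-only dip as non-CR. The effect could be near zero if such readings are rare.

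The confirmation issue is one of clarity: the protocol has two rules, and the SAP does not say which it implements or which tests confirm CR. Three stronger inferences fail:

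- An overstated CR rate is not shown.
- A shift of 4 points per subject (1/25) would use the primary-cohort cap, whereas the ITT figure is at most 2.3 points.
- Recasting CRs not confirmed at six months as partial responses has no basis in either document.

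The primary response rate counts both CR categories and partial response, so it and the 92% rule are not affected. The main HCL duration of response is also unaffected.

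**What to change.** - In SAP 2.6.1, make relapse as defined in Appendix 12 the event that ends HCL CR duration. State explicitly that death is added as an event, because Appendix 12 does not name it.
- Keep first non-CR assessment or death as a sensitivity analysis, including for the 180-day proportion.
- If the present rule stays as the main one, declare it in Section 3 and show both versions.
- Reconcile Appendix 12's two confirmation passages, and state in Table 2-4 which one is implemented and which tests are needed at the second assessment. The schedule lists immunoglobulins only for multiple myeloma, so the six-month check as written cannot be fully derived from scheduled HCL data; the reconciliation should say how that is handled.

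The cost is SAP wording, one added derivation and a second set of HCL CR-duration outputs. Relapse already feeds the HCL duration-of-response analysis, so that derivation needs no new data collection.

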- a decrease of the area of enhancing or non-enhancing lesion on T2 or FLAIR MR imaging between 25% and 50% compared with baseline
- no new lesions, no new T2 or FLAIR abnormalities apart from those consistent with radiation effect, and no new or increased enhancement; **and**
- subject should be on a corticosteroid dose that should not be greater than the dose at time of baseline scan, and should be stable or improved clinically

Stable disease (SD): Stable disease (SD) is present if the changes do not qualify for CR, PR, MR or progression and requires:

- stable area of enhancing or non-enhancing abnormalities on T2 or FLAIR imaging
- no new lesions, no new T2 or FLAIR abnormalities apart from those consistent with radiation effect, and no new or increased enhancement
- subject should be on a corticosteroid dose that should not be greater than the dose at time of baseline scan, and should be stable or improved clinically

Disease progression (PD): Disease progression (PD) is defined by any of the following:

- development of new lesions or increase of enhancement (radiological evidence of malignant transformation)
- a 25% increase in the sum of the products of perpendicular diameters of the T2 or FLAIR enhancing or non-enhancing lesion on stable or increasing doses of corticosteroids compared with baseline scan or best response after initiation of therapy, not attributable to radiation effect or to comorbid events
- definite clinical deterioration not attributable to other causes apart from the tumour, or decrease in corticosteroid dose;
- or failure to return for evaluation because of death or deteriorating condition, unless caused by documented non-related disorders

References:

van den Bent MJ, Wefel JS, Schiff D, et al. Response assessment in neuro-oncology (a report of the RANO group): assessment of outcome in trials of diffuse low grade gliomas. *The Lancet*. 2011;12:583-593.

21.14 Appendix 14: RANO Response Criteria: Updated Response Assessment Criteria for WHO Grade 3 and 4 Glioma

Measureable disease is defined as bidimensionally contrast-enhancing or enhancing lesions with clearly defined margins by magnetic resonance imaging (MRI) scan, with two perpendicular diameters of at least 10 mm, visible on 2 or more axial slices that are preferably, at most, 5 mm apart with 0 mm skip.

Non-measurable disease is defined as either unidimensionally measurable lesions, masses with margins not clearly defined, or lesions with maximal perpendicular diameters less than 10 mm.

All measurable and non-measurable lesions must be assessed using the same techniques as at baseline.

Complete response (CR): Requires all of the following:

- complete disappearance of all enhancing measurable and non-measurable disease sustained for at least 4 weeks
- no new lesions
- stable or improved non-enhancing (T2/FLAIR [fluid attenuated inversion recovery]) lesions
- subjects must be off corticosteroids (or on physiologic replacement doses only)
- stable or improved clinically.

Note: Subjects with non-measurable disease only cannot have a CR; the best response possible is stable disease (SD).

Partial response (PR): Requires all of the following:

- $\geq 50\%$ decrease compared with baseline, in the sum of products of perpendicular diameters of all measurable enhancing lesions sustained for at least 4 weeks
- no progression of non-measurable disease; no new lesions
- stable or improved non-enhancing (T2/FLAIR) lesions on same or lower dose of corticosteroids compared with baseline scan

- corticosteroid dose at the time of the scan evaluation should be no greater than the dose at time of baseline scan
- stable or improved clinically.

Note: Subjects with non-measurable disease only cannot have a PR; the best response possible is SD.

Stable disease (SD): Requires all of the following:

- does not qualify for CR, PR, or progression
- stable non-enhancing (T2/FLAIR) lesions on same or lower dose of corticosteroids compared with baseline scan.

In the event that the corticosteroid dose was increased for new symptoms and signs without confirmation of disease progression (PD) on neuro-imaging, and subsequent follow-up imaging shows that this increase in corticosteroids was required because of PD, the last scan considered to show SD will be the scan obtained when the corticosteroid dose was equivalent to the baseline dose.

NOTE: Stable doses of corticosteroids include subjects not on corticosteroids.

Disease progression (PD): Disease progression (PD) is defined by any of the following:

- $\geq 25\%$ increase in sum of the products of perpendicular diameters of enhancing lesions compared with the smallest tumor measurement obtained either at baseline (if no decrease) or best response, on stable or increasing doses of corticosteroids
- significant increase in T2/FLAIR non-enhancing lesion on stable or increasing doses of corticosteroids compared with baseline scan or best response after initiation of therapy not caused by co-morbid events (e.g., radiation therapy, demyelination, ischemic injury, infection, seizures, post-operative changes, or other treatment effects)
- any new lesion; clear clinical deterioration not attributable to other causes apart from the tumor (e.g., seizures, medication adverse effects, complications of therapy, cerebrovascular events, infection) or changes in corticosteroid dose
- failure to return for evaluation as a result of death or deteriorating condition

- clear progression of non-measurable disease.

Summary of RANO Response Criteria

Criterion	CR	PR	SD	PD
T1 gadolinium-enhancing disease	None	≥50% decrease	<50% decrease but <25% increase	≥25% increase ¹
T2/FLAIR	Stable or decrease	Stable or decreasing	Stable or decrease	Increase
New Lesion	None	None	None	Present
Corticosteroids	None	Stable or decreasing dose	Stable or Decreasing dose	NA ²
Clinical Status	Stable or increase	Stable or increase	Stable or increase	Decrease
Requirement for Response	All	All	All	Any

Abbreviations: CR = complete response; FLAIR = fluid-attenuated inversion recovery; NA = not applicable; PD = progressive disease; PR = partial response; RANO = Response Assessment in Neuro-Oncology; SD = stable disease

Progression occurs when this criterion is present.

Increase in corticosteroids alone will not be taken into account in determining progression in the absence of persistent clinical deterioration.

References:

Wen PY. Updated Response Assessment Criteria for High-Grade Gliomas: Response Assessment in Neuro-Oncology Working Group. *J Clin Oncol.* 2010;28(11):1963-1972.

